To achieve the aim of this study we will conduct a randomized controlled trial with three arms during May-Dec 2017. Participants will be Danish adults traveling on vacation in 2018 for a period of 1-3 weeks, recruited from the civil registration system. After enrollment and pretesting, participants will be randomly assigned to one of three experimental conditions. Three experimental groups will receive innovative intervention strategies for promoting sun protection practices during vacation – Protection Routine (1), Protection Routine (2) or both Protection Routine (1+2). The fourth experimental condition will be a minimal treatment control group. The primary outcomes of the trial will be a reduction in frequency of sunburn by adherence to the current sun protection advice from the Danish Cancer Society, i.e., use of shade, hats, protective clothing, and sunscreen as secondary outcomes. We hypothesize that the following two interventions will be able to reduce significantly the UVR exposure and risk of sunburns in Danes going on vacation to destinations with high UVI.

Protection routine 1

The existing evidence of sun protection against the detrimental effect of UV radiation shows that it is effective if performed correctly [26, 28]. We will develop a package of existing training and information and test if it will lead to better adherence. The package will include:

- The rationale of the prioritized sun advice [32]
- Activity planner, with suggestions to why a break from the sun is beneficial and how to plan activities before and after UVI maximum i.e. morning/early noon and afternoon/evening [32]
- Download of the UV-application ‘UVindeks’ for smartphones developed by the campaign and activating UV alert of geographic destination [33]
- A skin type guide

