A statistical power calculation shows that this sample size yields 95 % probability to detect a 10-percentage point drop from 50 % to 40 % in sunburn between an intervention group and the control group, and 80 % probability to detect a 7-percentage point drop from 50 % to 43 %. Our pilot study showed a 17-percentage point difference between our participants (32 %) relative to our annual sun surveys (49%). The number of invited participants to reach a final sample of ~2000 are included in the flow diagram in the protocol.

To obtain the final study sample size, we assumed 25 % of Danes invited to participate will volunteer for the project [41], >80 % will use of interventions (unpublished pilot study) and > 90 % will complete questionnaire [41, 42]. Loss to follow up after one year is expected to be 25 % according to travel patterns with high continuity of the Danes.

Multiple logistic regression analysis will be applied for analysis of differences in sunburn fraction. Analysis of variance will be used to analyze differences in sun protection score and UVR exposure score. Alpha criterion will be p=0.05 (two-tailed).

Intention-to-treat analysis will be applied by using multiple imputation by chained equations to account for missing information on sunburn among non-responders, using PROC MI in SAS 9.3. The imputation procedure includes variables hypothesized to potentially predict missing information (age, sex, education, skin type, sun behaviour, sun protection, sun intentions and intervention group). Analyses will be repeated including responders only and counting non-responders with same sunburn fraction as responders in the control group.

Clustering within families is not included in the planned analysis as it is unlikely to influence the results because participants from the same family have very low odds of being drawn with a total of 30.000 drawn out of the entire Danish population 18+ (app. 4.3 million).

Evaluation by validated questionnaire

Sun protective behavior, exposure to UVR and sunburn will be evaluated by use of a questionnaire validated by personal electronic UV-measurements [7, 43, 44]. This newly developed survey tool has made it possible in this project to evaluate the skin cancer interventions, without tracking of development of skin cancer which can take several years to develop after excessive UVR exposure. The short time period from intervention to evaluation minimizes recall bias.

Success criteria

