The primary success criteria of the effectiveness of the interventions is a 10 % decrease in sunburn fraction in the intervention groups as compared to the control group in the post-intervention measurement, as shown possible in the pilot study.

Furthermore, we aim to reach completion and response rates of no less than 90 % of the total sample, which we previously showed to be possible.

Secondary success criteria are increased awareness on the risk of skin cancer, increased use of protection (shade, clothes, hat and sunscreen) and decreased outdoor exposure when the UVI is highest between 12 and 3 pm. For all secondary success criteria, we aim for an improvement of 10 % between interventions and control group.

Potential bias

The randomization procedure ensures that all groups are similar; however, there is a risk of bias. The study population could be more or less likely to consist of sun seekers compared to the background population. This will not influence results of the trial because they should be equally distributed across the study arms. However, it could limit generalizability and influence future implementation of the interventions. The validated questionnaire allows us able to adjust for the received UV exposure of the participants in responder analyses.

Scientific and society perspectives and relevance

If the developed interventions are effective, they will be used in the Danish Sun Safety Campaign targeting Danes going on vacation to destinations with high UVI and thereby reduce the UVR exposure on a population level and eventually prevent skin cancers in Denmark. In addition, reductions in UVR exposure of the Danes will decrease the economic costs of skin cancer. The costs of skin cancer in Denmark were 250 million DKr annually during 2004-2008 [45]. While the return on investment (ROI) has not been estimated for Denmark, in Australia, the ROI for a campaign to prevent skin cancer was estimated to be 230 % [46].

Product and dissemination

The project will produce at least two scientific papers to document the effect of the study:

‘A randomized trial of Sun Safety Behavioral Interventions among Danes going to Sunny Destinations: Description and Baseline-study’

‘Sun Safety Behavioral Interventions among Danes going to Sunny Destinations: A Randomized Trial’

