The evaluation will be conducted in the online survey system, SurveyXact, provided by Rambøll. The system is used in numerous evaluations of the Danish Cancer Society. The evaluation is based on the validated UV behavior questionnaire recently developed by Danish Sun Safety Campaign. The questionnaire will be adapted to the trial.

[figure not shown]
Preparation of interventions

An intensive intervention package was developed prior to the study. The package is composed by known elements from the Danish Sun Safety campaign. The package also includes download of the UV-App developed by the Danish Sun Safety Campaign. The app includes an alert function for high UV-Indexes and can be adapted to the correct location by GPS or a selected city around the world. This mobile app is fully developed and available for this trial. The participants randomized to the package will receive alerts to take precautions against solar UVR before and during their vacation.

Invitations

The invitations for the project will be handled (printed, enveloped and sent) by trained volunteers from the Danish Cancer Society. Participants will sign up for the project on a developed web-page of the project. On the project homepage the participants will fill in a short form of contact information, demographic information, departure and arrival dates of their upcoming vacation and baseline sun behavior information for non-responder analyses. Participants who have not yet planned their vacation are instructed to contact the project team

Flow Diagram

once they have planned it. Likewise they will be reminded every 2-3 weeks during the period by mail or phone. Repeated invitations will be sent after two and four weeks to non-responders. Afterwards, participants will be contacted by the volunteers by phone to confirm their participation and receive information about the study. A student will be dedicated in organizing workflow of the volunteers and participate in the training of the volunteers. We have good experiences with this procedure from other projects like www.mituv.dk and www.statusd.dk also funded by TrygFonden.

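### The sun protection and UVR exposure scores get an unadjusted analysis of variance with no missing-data rule, while intention-to-treat imputation is defined for sunburn only

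*Combined protocol and SAP*

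**What the plan says.** All points are from the combined protocol and SAP.

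- **Statistical methods and power calculations, the scores.** Sunburn is assigned multiple logistic regression. For the two scores: "Analysis of variance will be used to analyze differences in sun protection score and UVR exposure score". No covariates and no handling of missing questionnaires are named for them.
- **Same section, intention-to-treat.** It is carried out by "using multiple imputation by chained equations to account for missing information on sunburn among non-responders". The imputation uses "variables hypothesized to potentially predict missing information (age, sex, education, skin type, sun behaviour, sun protection, sun intentions and intervention group").
- **Same section, sensitivity.** "Analyses will be repeated including responders only and counting non-responders with same sunburn fraction as responders in the control group". The second rule can only be applied to sunburn.
- **Invitations.** The sign-up form collects "baseline sun behavior information for non-responder analyses". The Time Schedule also lists a baseline questionnaire.
- **Potential bias.** The questionnaire is said to make it possible to "adjust for the received UV exposure of the participants in responder analyses".
- **Intervention study.** The protection behaviours, "use of shade, hats, protective clothing, and sunscreen as secondary outcomes", sit below sunburn in the hierarchy.

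No section says that the scores are imputed or adjusted for baseline.

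**The concern.** Sunburn, protection and exposure all come from one questionnaire sent after return (Evaluation by validated questionnaire; Data collection and handling). Someone who does not reply is therefore missing for all of them. For sunburn the plan fills the gap. For the scores it is silent, and an analysis of variance with no rule simply drops that person.

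Behaviour scores are where selective reply is most likely to matter, because the suspected predictors of missing information include the person's own sun behaviour and protection. Unequal reply between arms is also plausible. Intervention participants receive a hat, or an app with alerts and reminders, while controls receive only the basic advice.

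At stake is the evidence on how any change in sunburn came about. As written, sunburn would be reported on the randomised set and the scores on those who replied, with a possible score difference that reflects who replied.

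**Working it through.** The plan gives no figure on this point to reproduce. Its power figures concern sunburn and do not bear on it.

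**Inputs from the documents.** There are 1,980 completing participants, an expected completion above 90 %, and two-sided alpha of 0.05. At 90 % reply, 1,980 / 0.90 = 2,200 randomised. The text describes three interventions and a control, although it also speaks of three arms, and the flow diagram is not shown. With four equal arms (assumed), 2,200 / 4 = 550 per arm.

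**Assumed inputs.** The documents give none of these: correlation 0.6 between baseline and post-trip score, no true effect, log-odds of reply rising by β = 0.5 or 0.7 per SD of baseline protection, and the reply rates by arm.

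**Model.** Baseline X ~ N(0,1). Post-trip score Y = 0.6X + 0.8e, since √(1 − 0.36) = 0.8. Reply probability in arm a is p_a(X) = expit(α_a + β_a X), with α_a set to give the stated reply rate r_a.

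- Responder mean of baseline: m_a = E[X p_a(X)] / E[p_a(X)], by numerical integration.
- Bias (intervention minus control) = 0.6 (m_I − m_C).
- SE = √(v_C/(550 r_C) + v_I/(550 r_I)), where v_a = 0.36 Var(X | reply) + 0.64, slightly below 1.
- False-positive rate = Φ(−1.96 + |bias|/SE) + Φ(−1.96 − |bias|/SE).

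| Reply, control v intervention | β | m_C | m_I | Bias (SD) | SE | False positives |
|---|---|---|---|---|---|---|
| 90 % v 90 % | 0.5, both arms | 0.0488 | 0.0488 | 0 | 0.063 | 5.0 % |
| 87 % v 93 % | 0.5, both arms | 0.0632 | 0.0344 | −0.017 | 0.063 | 5.9 % |
| 87 % v 93 % | 0.7, both arms | 0.0860 | 0.0473 | −0.023 | 0.063 | 6.6 % |
| 85 % v 95 % | 0.5, both arms | 0.0726 | 0.0247 | −0.029 | 0.063 | 7.4 % |
| 85 % v 95 % | 0.7, both arms | 0.0986 | 0.0341 | −0.039 | 0.063 | 9.4 % |
| 80 % v 95 % | 0.5, both arms | 0.0962 | 0.0247 | −0.043 | 0.064 | 10.2 % |
| 80 % v 95 % | 0.7, both arms | 0.1299 | 0.0341 | −0.058 | 0.064 | 14.6 % |
| 85 % v 95 % | 0.5, control only | 0.0726 | 0 | −0.044 | 0.063 | 10.5 % |
| 85 % v 95 % | 0.7, control only | 0.0986 | 0 | −0.059 | 0.063 | 15.4 % |

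In these cases the bias runs against the intervention, because control responders are the more selected group. The opposite reply pattern reverses the sign.

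**When there is no bias.** If reply depends on arm alone, or on behaviour alone and equally in both arms, then m_I = m_C. The same holds if arm and behaviour act multiplicatively on the reply probability, p = g(arm) × h(X): g cancels from m_a. At 90 % v 76 % reply with a common multiplicative gradient, the bias was 0.

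**Scale.** The difference detectable with 80 % power and 495 responders per arm is (1.96 + 0.84) × √(2/495) = 0.18 SD. A bias of 0.02 SD is about a tenth of that, and 0.06 SD about a third.

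**Baseline-adjusted analysis.** In 4,000 simulated trials per scenario, adding X to the model gave bias within 0.001 SD and false positives of 4.6–5.5 % throughout. At 90 % reply the SE of the arm difference falls from √(2/495) = 0.064 (simulated 0.063) to 0.8 × 0.064 = 0.051.

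**Imputation followed by an unadjusted comparison.** With many imputations at 90 % reply, SE ≈ √((2/550)(0.36 + 0.64/0.9)) = √(0.003636 × 1.071) = 0.062. The bias goes, but the precision gained by adjustment does not appear.

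**The case against.** The strongest reply is that this is silence on secondary outcomes, and that several inferences from it go too far.

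- **A reader might infer that the plan expects arm and baseline behaviour to drive non-response.** It does not say so. The variables are only hypothesized as possible predictors of missing information, which can also mean predictors of the missing values. Including the arm in an imputation model is routine. The list is not labelled as baseline either, although the sign-up data make that the natural reading. If post-trip measures were meant, chained equations would fill them in too, but nothing says the analysis of variance would use the filled-in scores.
- **A reader might infer that dependence of reply on arm and behaviour is enough for bias.** It is not. The two must combine other than multiplicatively, and the documents do not predict how they combine.
- **A reader might infer that the plan prescribes a responder-only comparison of scores.** That is the practical result of giving no rule. The planned responder-only repeat is worded in the plural and is not expressly confined to sunburn.
- **A reader might extend the point to every secondary success criterion.** Analysis of variance is assigned to the two scores only. Awareness, individual behaviours and midday exposure have no stated test.

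The differing-populations worry is also partly met, because the responder-only sunburn result can be set beside responder-only scores. And at the plan's target of at least 90 % reply, the bias is small unless reply differs by arm.

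All of this limits wording and size. It does not supply a method for the scores. The Confounders section lists sun-seeking behaviour, but no section puts it into the score analysis. The adjustment mentioned under Potential bias is for UV exposure received, which is measured after the intervention and is no substitute for a baseline covariate.

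**Conclusion.** The point stands as a gap in the analysis of two secondary outcomes. The imputation covers sunburn only. The scores get an unadjusted comparison that in practice uses responders, although baseline data suited to a better analysis are already collected.

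The size is conditional. With a correlation of 0.6, 550 randomised per arm and slopes of 0.5–0.7, the bias is nil with balanced reply and a common slope, about 0.02 SD (6–7 % false positives) at 87 % v 93 %, 0.03–0.04 SD (7–9 %) at 85 % v 95 %, and 0.04–0.06 SD (10–15 %) at 80 % v 95 %. If behaviour drives reply in the control arm only, it is 0.04–0.06 SD (10–15 %) at 85 % v 95 %. The 80 % v 95 % case averages 87.5 % reply, below the plan's own target, and the control-only slope is the least supported assumption.

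Nothing here touches the sunburn analysis, and the documents do not show that the score results will be biased. The change is worth making because it is cheap, guards against the bias if reply proves uneven, and improves precision in any case.

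**What to change.** 1. Analyse the sun protection and UVR exposure scores with a covariate-adjusted analysis of variance that includes the baseline sun behaviour, protection and intention variables. State in the plan that the variables in the imputation list are the baseline values.
2. Add the two post-trip scores to the existing PROC MI model and apply the same adjusted analysis to the imputed data, so that the scores are reported on the same intention-to-treat set as sunburn. Imputation followed by an unadjusted comparison is not enough, because it gives up the precision. With only the outcome missing and the same covariates, it is the adjustment that removes the bias. The imputation supplies the matching analysis set.
3. Keep the responder-only analysis of the scores as sensitivity, as for sunburn, and report reply by arm.

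The cost is one or two sentences in the plan and slightly more analysis work. No new data are needed, provided that the baseline questionnaire holds the protection and intention items that the imputation list implies. Writing it down before analysis also removes a choice that could otherwise be made after seeing the results.

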- A newly developed instruction for correct application of sunscreen [40]

Denmark is not a hat-wearing society. By making smart design hats available and attractive may increase this sun protection behavior, which has large potential in prevention of skin cancer (**ibid: p2**). A very simple study showed that a brief instruction to sunscreen application increased the provided protection significantly [40].

Protection routine 1+2

The group will receive both above mentioned interventions and will reveal potential dose response effects from level of protection.

Control group

All groups including the control group will receive a minimal intervention with the current sun advice from the Danish Sun Safety Campaign.

Study population

The participants of the study are recruited from the Danish civil registration based system. The study population will represent all groups of the Danish population. Eligibility criteria for the project are persons living in Denmark going on vacation in May-December 2018 and having a smartphone compatible with either apple iOS (version 7.0 or newer) or Google Android (version 4.0 or newer). The period May to December is chosen as it includes all types of vacationers. The summer vacation constitutes the majority of the sunny vacations of the Danes. The period includes both the summer, where Danes typically travel to the Mediterranean area and the winter period where travel patterns change a bit to more exotic areas like Thailand, Egypt and the Canarias Islands. Exclusion criteria are persons younger than 18 years of age.

Randomization

The participants will be randomized to one of the intervention groups or to the minimal-treatment control group. The randomization procedure is described in the protocol.

Confounders

Possible confounders includes age, gender, education, skin type, skin cancer history, nevi, sun-seeking behavior and number of sunny vacations in past 5 years [28].

Statistical methods and power calculations

The number of completing participants (n= 1.980) is based on a power calculation, recruitment for similar studies conducted by the applicant [41, 42] and our recent pilot study (unpublished, summarized in the end of this application).

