Invitations will be identical for all invited potential participants. It will include invitation to participate in a project about how the Danish Cancer Society can improve their knowledge about sun protection information and that they will be allocated to use a specific sun protection during their vacation. It will also include information about which procedures may be applied.

Recruitment

The invited participants will provide their contact data and supplemental background data upon recruitment on the project homepage. Only one person from a family will be enrolled in the study.

Development of protection routines and training package intervention

The final information package is composed by various elements from the Danish Sun Safety campaign as described in the project description. The package was created by an experienced group from the Danish Sun Safety Campaign, including experts in public health, anthropology and communication and was be piloted before the trial.

Main study

The participants will be randomized to one of the three groups below after agreeing to participate. The detailed distribution of participants are shown in the flow diagram. The randomization will be stratified by gender (Male/Female), age group (18-25, 26-35, 36-45, 46-55, 56-65 and 65+) and region (Capital, Zealand, Northern Jutland, Central Jutland and Southern Denmark). The randomization procedure will be blind to the researcher. All participants will be contacted immediately before their vacation and will receive their intervention package before departure.

Control group – Minimal intervention

All groups including the control group will receive a minimal intervention with the sun advice from the Danish Sun Safety Campaign.

Protection Routine 1 – Intensive information and training in current sun advice

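### The variables named for imputing sunburn omit region, skin cancer history, nevi and perhaps past sunny vacations; adding them costs almost nothing and makes the missing-at-random assumption more credible

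*Combined protocol and SAP*

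**What the plan says.** Under *Statistical methods and power calculations*, the main sunburn comparison is described in one sentence: "Multiple logistic regression analysis will be applied for analysis of differences in sunburn fraction". No covariates are listed for that model. Intention-to-treat is implemented by "using multiple imputation by chained equations to account for missing information on sunburn among non-responders". The predictors are introduced with "The imputation procedure includes variables hypothesized to potentially predict missing information" and then given as "age, sex, education, skin type, sun behaviour, sun protection, sun intentions and intervention group". Two repeat analyses follow: "Analyses will be repeated including responders only and counting non-responders with same sunburn fraction as responders in the control group".

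The section *Confounders* states: "Possible confounders includes age, gender, education, skin type, skin cancer history, nevi, sun-seeking behavior and number of sunny vacations in past 5 years". It does not say that these enter the primary model.

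Under *Main study*: "The randomization will be stratified by gender (Male/Female), age group" "and region (Capital, Zealand, Northern Jutland, Central Jutland and Southern Denmark".

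Under *Invitations*, demographic data and baseline sun behaviour are collected at sign-up for use in non-responder analyses. The documents do not say whether skin cancer history, nevi and past sunny vacations are recorded then.

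**The concern.** Sunburn is the primary outcome, and imputation is how everyone randomized is kept in its analysis. An imputation model should hold at least the variables of the analysis model. If a variable predicts both sunburn and non-response and is left out, imputed values are drawn as though, given the included variables, it had no bearing on sunburn. The plan names skin cancer history, nevi and past sunny vacations as possible confounders and stratifies on region, yet names none of them as imputation predictors and gives no reason.

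What is at stake is the arm difference in sunburn. The arms differ in what participants receive, from minimal advice to a combined package of information, app, hat and sunscreen instruction. Non-response could therefore differ between them.

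**Working it through.** **1. The three lists side by side**

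| Variable | Possible confounder | Stratum | Named for imputation |
|---|---|---|---|
| Age | yes | yes | yes |
| Gender | yes | yes | yes |
| Education | yes | – | yes |
| Skin type | yes | – | yes |
| Sun-seeking | yes | – | plausibly, as sun behaviour |
| Past sunny vacations | yes | – | unclear, may fall under sun behaviour |
| Skin cancer history | yes | – | no |
| Nevi | yes | – | no |
| Region | – | yes | no |

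Intervention group is in the imputation list, so each arm's missing values are imputed with their own arm effect.

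**2. Formula for the bias**

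The plan gives no figure to reproduce here. From the plan: sunburn 50% in control and 40% under intervention, and more than 90% questionnaire completion, so about 10% missing. Assumed, because the documents give nothing: an omitted binary predictor U, its prevalence, its odds ratio (OR) for sunburn, and its link to non-response. U is taken as unrelated to the included variables.

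In an arm with true sunburn fraction p, let w be the share at each level of U, r the response probability and s the sunburn risk. Imputation without U tends to the responders' fraction:

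m = Σ(w·r·s) / Σ(w·r)

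Bias in the difference = (m₁ − p₁) − (m₀ − p₀), with 1 for intervention and 0 for control.

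**3. Worked case: prevalence 30%, OR 2, non-response doubled when U = 1, 10% missing**

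- Non-response is 0.10/1.3 = 0.0769 for U = 0 and 0.1538 for U = 1.
- Intervention: s = 0.3495 and 0.5179. m = (0.7×0.9231×0.3495 + 0.3×0.8462×0.5179)/0.90 = 0.3970, which is 0.30 points below 0.40.
- Control, same pattern: s = 0.4488 and 0.6195, m = 0.4969, which is 0.31 points below 0.50. The two errors cancel and the net bias is below 0.01 points.
- Control, non-response unrelated to U: no error in control, net bias −0.30 points.
- Control, non-response halved when U = 1: 0.10/0.85 = 0.1176 and 0.0588, m = 0.5023, net bias −0.54 points.

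**4. Range over prevalence 5–50% and OR 1.5–3 (absolute bias, points)**

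| Non-response pattern | 10% missing | 28% missing |
|---|---|---|
| Same in both arms | at most 0.02 | at most 0.08 |
| Depends on U in intervention only | 0.05–0.48 | 0.18–1.67 |
| Opposite directions by arm | 0.08–0.97 | 0.27–3.40 |

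The 28% column is a stress case (1 − 0.80×0.90, treating non-use of the intervention as non-response), not the plan's expectation.

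**5. A stronger, continuous omitted predictor**

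Assumed: non-response odds double per SD. The true difference is −10 points.

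| Pattern | Log-odds 0.7 per SD for sunburn | Log-odds 0.35 per SD |
|---|---|---|
| Same pattern, 10% missing in both arms | −10.0 | −10.0 |
| Intervention only, 10% missing | −11.0 | −10.5 |
| Intervention only, 20% missing | −12.0 | −11.1 |
| Same pattern, 10% control vs 20% intervention | −11.0 | −10.5 |

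The last row shows that unequal rates alone are enough, even when non-response depends on the predictor in the same way in both arms. With log-odds 0.7 and milder non-response odds ratios (1.5 intervention, 1.2 control), the bias at 10% missing is about 0.3 points.

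**6. Finite-sample check**

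Simulated multiple imputation used 495 per arm (1,980/4, assuming equal allocation to four groups), 400 replicates, 10 imputations, and U as in step 3, with 10% missing. Bias with U omitted and then included: −0.03 and −0.02 (same pattern), −0.27 and −0.04 (intervention only), −0.46 and 0.00 (opposite). Including U removes essentially all of it.

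For scale, the standard error of the difference is √(0.25/495 + 0.24/495) = 3.15 points.

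**The case against.** The strongest case against has four parts.

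- **The list is not declared complete.** It is introduced by a verb of inclusion, and sun behaviour may cover past vacations. This stands. Clear non-mention is limited to region, skin cancer history and nevi.
- **No mismatch of models is shown.** The covariates of the logistic model are never listed, and the confounders are called only possible ones. This stands too, so the mismatch is conditional on what enters that model.
- **A planned repeat analysis may already protect.** If the logistic model does adjust for the omitted variables, the responders-only repeat adjusts for them as well. A simulation of the step 5 pattern (log-odds 0.7, intervention only, 10% missing) gave an adjusted responders-only difference of −10.05 points against −10.01 in full data. That is a real safeguard, but only in a secondary analysis. Unadjusted, responders-only carries about the same bias as imputation without the variable (−0.47 vs −0.46). Giving non-responders the control fraction shrinks a true 10-point difference to 10×(1 − 0.10) = 9.0; it is a conservative bound, not a correction.
- **The size depends on assumed inputs.** If the included variables explain 30% or 50% of the strong predictor in step 5, the bias of about 1.1 points found in that simulation falls to about 0.75 or 0.6. Skin type and sun intentions are already included, so some overlap is likely.

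A reader might infer that the imputation as planned biases the arm comparison and overstates the benefit. The documents do not support that. They contain no evidence that non-response differs by arm, and reversing the assumed direction moves the bias toward no effect by the same amount.

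**Conclusion.** The point holds as a small improvement to the specification, not as a demonstrated bias. Region, skin cancer history and nevi are not named as imputation predictors, and past sunny vacations are named only if sun behaviour is taken to include them. Bias in the arm difference needs an omitted variable that predicts sunburn beyond the included ones, together with non-response whose rate, or whose dependence on that variable, differs by arm. At the planned 10% non-response it is about 1 point or less under the inputs assumed here, roughly a third of the standard error and a tenth of the target difference. It is essentially zero if non-response is alike in all arms. Larger figures, up to 3.4 points, need both much higher and strongly arm-dependent non-response than the plan expects.

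**What to change.** - List the covariates of the primary logistic model.
- Put region and every one of those covariates into the PROC MI model. Include skin cancer history, nevi and past sunny vacations where they are recorded at baseline.
- Define sun behaviour, and state that it and sun protection are baseline measures when used to impute for non-responders. Post-vacation answers are missing for the same people whose sunburn is missing, so they cannot inform those imputations.
- Confirm whether the three confounder items were asked at sign-up.

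The cost is a longer variable list and a sentence or two in the plan. Region must be known for everyone randomized because it is a stratum, so it needs no new data. The other three need none if they were asked at baseline; if they were not, the plan should say so. The change should be fixed before outcome data are compared by arm.
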